6.3 SAFETY MONITORING DAYS 3-6

The following assessments will be completed daily during the safety monitoring period until the primary Safety Review on Day 7 if patient is still in the administering unit.

- Physical Exams: Abbreviated, targeted physical examinations (i.e., assessments of the skin, respiratory, cardiovascular system, and abdomen (liver and spleen), will be performed at time points specified in the Schedule of Activities (Section 1) and will be based on the subject's clinical status and what the clinic staff deem is appropriate.
- Concomitant medications
- Clinical End-point Assessment includes: Survival (Y/N), On mechanical ventilation (Y/N), In ICU (Y/N), In Hospital (Y/N), Use of anti-coagulation (drug, dose, intent: prophylaxis vs therapeutic), WHO Ordinal Score (See Appendix D for scale). If patient is in ICU then the following assessment will be completed: Sequential Organ Failure Assessment (SOFA), PaO₂/FiO₂, following ventilation parameters (as applicable): type of ventilation (CPAP, BiPAP, or intubation)/ ventilation rate/ pulse/ tidal volume/ positive end-expiratory pressure (PEEP), recording of vasoactive drugs and renal support, recording of supportive interventions that can impact clinical endpoints (use of prone ventilation, use of paralytics, use of pulmonary vasodilators, use of corticosteroids, use of oral decontamination and raising the head of the patient to at least 30° to prevent ventilator-associated pneumonia)
- Vital Signs: include core temperature, mean arterial pressure (mmHg), pulse (beats/min), respiratory rate (breaths/min).
 - The same method for assessing temperature should be used at all visits until patient is discharged from the administering unit, if possible.

- CBC with differential: Samples should be taken in the morning between 04:00 and 10:00 using the values closest to 10:00. (mandatory for Arm 1, only if done as part of standard of care for Arm 2)
- Serum chemistry (mandatory for Arm 1, only if done as part of standard of care for Arm 2):
 - Samples should be taken in the morning between 04:00 and 10:00 using the values closest to 10:00.
 - Chemistry includes Glucose, Ca, Mg, Phos, ALP, Albumin, Total Protein, Total Bilirubin, K, Na, Cl, HCO₃, BUN, Cr, ALT, AST, LDH, Amylase.
- CRP, ferritin, D-Dimer (mandatory for both Arms).
- Urinalysis: Samples should be taken in the morning between 04:00 and 10:00 using the values closest to 10:00. (mandatory for Arm 1, only if done as part of standard of care for Arm 2)
- Research blood collection: At least once between Day 3 and Day 6. All protocol required research blood collection assessments must be conducted in accordance with Laboratory Manual.
- Exploratory Bronchoalveolar lavage: **Should be done at least once during this period if it was performed prior to administration of cells.** If BAL is not performed then tracheal aspirate or sputum (induced or expectorated).
- Chest Imaging: CT scan or Chest X-Ray. Once between Days 1-6.
- AE review and evaluation
- PT/INR, PTT (Should be done at least once during this period, for patients in both Arms).

6.4 PRIMARY SAFETY REVIEW (DAY 7)

Primary Safety Review is on Day 7 or on last day of stay in the administering unit, whichever comes earlier. In Arm 1, upon completion of Primary Safety Review assessments, the Principal Investigator and the Medical Monitor will review the data.

- Physical Exams: Abbreviated, targeted physical examinations (i.e., assessments of the skin, respiratory, cardiovascular system, and abdomen (liver and spleen), will be performed at time points specified in the Schedule of Activities (Section 1) and will be based on the subject's clinical status and what the clinic staff deem is appropriate.
- Concomitant medications
- Clinical End-point Assessment includes: Survival (Y/N), On mechanical ventilation (Y/N), In ICU (Y/N), In Hospital (Y/N), Use of anti-coagulation (drug, dose, intent: prophylaxis vs therapeutic), WHO Ordinal Score (See Appendix D for scale). If patient is in ICU then the following assessment will be completed: Sequential Organ Failure Assessment (SOFA), PaO₂/FiO₂, following ventilation parameters (as applicable): type of ventilation (CPAP, BiPAP, or intubation)/ ventilation rate/ pulse/ tidal volume/ positive end-expiratory pressure (PEEP), recording of vasoactive drugs and renal support, recording of supportive interventions that can impact clinical endpoints (use of prone ventilation, use of paralytics, use of pulmonary vasodilators, use of corticosteroids, use of oral decontamination and raising the head of the patient to at least 30° to prevent ventilator-associated pneumonia)
- Vital Signs: include core temperature, mean arterial pressure (mmHg), pulse (beats/min), respiratory rate (breaths/min).
 - The same method for assessing temperature should be used at all visits until patient is discharged from the administering unit, if possible.

- CBC with differential: Samples should be taken in the morning between 04:00 and 10:00 using the values closest to 10:00 (mandatory for Arm 1, only if done as part of standard of care for Arm 2).
- Serum chemistry (mandatory for Arm 1, only if done as part of standard of care for Arm 2):
 - Samples should be taken in the morning between 04:00 and 10:00 using the values closest to 10:00.
 - Chemistry includes Glucose, Ca, Mg, Phos, ALP, Albumin, Total Protein, Total Bilirubin, K, Na, Cl, HCO₃, BUN, Cr, ALT, AST, LDH, Amylase.
- CRP, ferritin, D-Dimer (mandatory for both Arms).
- Urinalysis: Samples should be taken in the morning between 04:00 and 10:00 using the values closest to 10:00 (mandatory for Arm 1, only if done as part of standard of care for Arm 2).
- Research blood collection: All protocol required research blood collection assessments must be conducted in accordance with Laboratory Manual.
- Exploratory Bronchoalveolar lavage: **Should be done only if not performed at least once after administration of cells while a sample was collected prior to treatment with cells.** If BAL is not performed then tracheal aspirate or sputum (induced or expectorated).
- Chest Imaging: CT scan (preferred) or Chest X-Ray. Imaging done on Day 6 or Day 8 will be accepted.
- AE review and evaluation.

6.5 SHORT-TERM FOLLOW-UP (DAY 14, 21 AND 28)

If patient is discharged from the hospital, Day 14 and 21 visits can be omitted. Day 28 visit can be the day of discharge from the hospital if it is earlier.

- Physical Exams: Only if patient is in the the administering unit, abbreviated, targeted physical examinations (i.e., assessments of the skin, respiratory, cardiovascular system, and abdomen (liver and spleen)), will be performed at time points specified in the Schedule of Activities (Section 1) and will be based on the subject's clinical status and what the clinic staff deem is appropriate.
- Concomitant medications
- Clinical End-point Assessment includes: Survival (Y/N), On mechanical ventilation (Y/N), In ICU (Y/N), In Hospital (Y/N), Use of anti-coagulation (drug, dose, intent: prophylaxis vs therapeutic), WHO Ordinal Score (See Appendix D for scale). If patient is in ICU then the following assessment will be completed: Sequential Organ Failure Assessment (SOFA), PaO₂/FiO₂, following ventilation parameters (as applicable): type of ventilation (CPAP, BiPAP, or intubation)/ ventilation rate/ pulse/ tidal volume/ positive end-expiratory pressure (PEEP), recording of vasoactive drugs and renal support, recording of supportive interventions that can impact clinical endpoints (use of prone ventilation, use of paralytics, use of pulmonary vasodilators, use of corticosteroids, use of oral decontamination and raising the head of the patient at least 30° to prevent ventilator-associated pneumonia)
- Vital Signs: include core temperature, mean arterial pressure (mmHg), pulse (beats/min), respiratory rate (breaths/min).
 - The same method for assessing temperature should be used at all visits for each individual subject, if possible.
- CBC with differential. Only if performed as Standard of Care.
- Serum chemistry. Only if performed as Standard of Care:

- Chemistry includes Glucose, Ca, Mg, Phos, ALP, Albumin, Total Protein, Total Bilirubin, K, Na, Cl, HCO₃, BUN, Cr, ALT, AST, LDH, Amylase.
- Chest Imaging: CT scan (preferred on Day 28) or Chest X-Ray. Only if performed as Standard of Care.
- AE review and evaluation
- Research blood collection: Only if patient is in the administering unit. All protocol required research blood collection assessments must be conducted in accordance with Laboratory Manual.

6.6 LONG-TERM FOLLOW-UP (DAY 90± 14)

On Day 90± 14 days, an in-person visit, or telemedicine will be arranged to complete the assessments listed below. If any of the laboratory assessments cannot be performed due to inability to arrange a blood collection, it will not be considered as protocol deviation.

- Physical Exams: Abbreviated, targeted physical examinations (i.e., assessments of the skin, respiratory, cardiovascular system, and abdomen [liver and spleen]), will be performed at time points specified in the Schedule of Activities (Section 1) and will be based on the subject's clinical status and what the clinic staff deem is appropriate.
- Concomitant medications
- Clinical End-point Assessment includes: Survival (Y/N), On mechanical ventilation (Y/N), In ICU (Y/N), In Hospital (Y/N), Use of anti-coagulation (drug, dose, intent: prophylaxis vs therapeutic), WHO Ordinal Score (See Appendix D for scale). If patient is in ICU then the following assessment will be completed: Sequential Organ Failure Assessment (SOFA), PaO₂/FiO₂, following ventilation parameters (as applicable): type of ventilation (CPAP, BiPAP, or intubation)/ ventilation rate/ pulse/ tidal volume/ positive end-expiratory pressure (PEEP), recording of vasoactive drugs and renal support, recording of supportive interventions that can impact clinical endpoints (use of prone ventilation, use of paralytics, use of pulmonary vasodilators, use of corticosteroids, use of oral decontamination and raising the head of the patient at least 30° to prevent ventilator-associated pneumonia)
- Vital Signs: include core temperature, mean arterial pressure (mmHg), pulse (beats/min), respiratory rate (breaths/min).
- Research blood collection: Can be omitted if visit is telemedicine. All protocol required research blood collection assessments must be conducted in accordance with Laboratory Manual
- AE review and evaluation

7 STUDY INTERVENTION

7.1 STUDY INTERVENTION(S) ADMINISTRATION

7.1.1 STUDY INTERVENTION DESCRIPTION

Descartes-30 is an allogeneic human MSC product modified to transiently express two human DNase enzymes that degrade NETs.

7.1.2 DOSING AND ADMINISTRATION

7.1.2.1 PRE-INFUSION MONITORING AND DELAY OF CELL INFUSION

[figure not shown]
Infusions can be delayed up to 96 hours based on PI discretion. Prior to all Descartes-30 infusions, patients should be observed for 2 hours (\pm 30 min) to document their stability by meeting the following parameters and based on PI's best clinical judgement:

1. Patient is not requiring a change in ventilator settings
2. Stable use of vasopressors if the patient required vasopressors for blood pressure support.
Stable use is defined as increasing no more than 50% of baseline recorded at initiation of monitoring.

During 2-hour monitoring, following parameters should be recorded at least every 30 min: ventilation variables [type of ventilation (CPAP, BiPAP, or intubation), ventilation rate, pulse, tidal volume, positive end-expiratory pressure (PEEP)], recording of vasoactive drugs and renal support and vital signs [include core temperature, mean arterial pressure (mmHg), pulse (beats/min), respiratory rate (breaths/min)]. If patients do not meet stability criteria for 2 hours, infusion can be delayed for up to 96 hours. If infusion is delayed, the patient will be periodically monitored to assess stability. If infusion is delayed more than 96 hours due to medical instability, patients will come off study treatment. Infusions can also be delayed up to 96 hours in case of a holiday or by PI's discretion.

Patients experiencing toxicities that are probably or definitely related to Descartes-30 will have their next Descartes-30 dose delayed until these toxicities have resolved to at least Grade 2, unless in the documented opinion of the site Principal Investigator and the medical monitor it is reasonable to proceed. During this period, patients will be assessed to record adverse events and decide whether the patient meets criteria for cell infusion. The discussions between the Medical Monitor and site Principal Investigator will be documented. If a dose is delayed for more than 96 hours, the patient will come off study treatment.

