Patients diagnosed with ARDS or PNA will undergo screening during which informed consent will be obtained and eligibility assessed. Up to 7 or 14 days may elapse between confirmation of PNA or ARDS diagnosis respectively and administration of the first infusion of study product. Patients will be dosed once per day for 3 consecutive days (Day 0, 1, 2). In Arm 1 (Dose Escalation), patients were monitored for 7 days after the first Descartes-30 infusion (unless they are discharged from the administering unit prior to Day 7) with a safety review on Day 7 (or last day in the administering unit, whichever comes earlier) to determine whether the next patient in the trial can be dosed. In Arm 2 (Dose Expansion), patients will be enrolled consecutively to receive treatment on Day 0, 1, and 2 at a dose up to the MTD determined in Arm 1. For both Arms, there will be an optional visit on Days 14 and 21 and a mandatory visit on Day 28. Long-term follow-up will occur at Day 90 (in-person or telephone contact).

Study Intervention:

The study product will be manufactured from qualified allogeneic donors under GMP standards. After the product passes Quality Control, it will be shipped to the study site for storage. Patients will receive the first dose of Descartes-30 cells via intravenous administration within 14 days of diagnosis of ARDS or within 7 days of diagnosis of PNA. Patients will receive two more infusions over the following 2 days unless they meet the criteria for holding dose or discontinuing study treatment.

In the dose escalation arm (Arm 1), the following doses of Descartes-30 cells are planned:

- Dose Level 1: 100 million cells administered on Days 0, 1 and 2
- Dose Level 2: 300 million cells administered on Days 0, 1 and 2
- Dose Level 3: 600 million cells administered on Days 0, 1 and 2

- Dose Level 4: 1200 million cells administered on Days 0, 1 and 2

An additional 12 patients per cohort (ARDS or PNA) may be enrolled at a dose up to MTD.

Study Duration: 30 months

Participant Duration: 3 months

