4.5 DOSE ESCALATION STOPPING RULES

The Medical Monitor will apply the following rules to determine if it is safe to proceed to the next Dose Level, or if dose escalation should stop. Pre-specified rules for pausing or stopping the whole study are described in Section 8.5 and rules for individual patient withdrawal are described in Section 8.4.

Should one of three patients in a Dose Level experience dose-limiting toxicity (DLT, see Section 8.1.2 for definition) within 7 days after receiving the first dose of the cells that is considered probably or definitely related to Descartes-30, 3 more patients will be enrolled and treated at that Dose Level. If only 1/6 of patients at that Dose Level has a DLT, and if the medical monitor agrees, treatment will proceed to the next higher Dose Level. If 2 or more out of 3 to 6 patients develop a DLT, no further patients will be dosed at that dose level. The MTD will be defined as the highest dose at which a maximum of 1 of 6 patients has a DLT. In Arm 2, up to 12 more patients who meet the eligibility criteria may be treated in each cohort (ARDS and PNA) at a dose up to MTD, provided that the medical monitor approves the enrollment of each such patient based on ongoing review of the cumulative safety data.

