7.1.2.5 CRITERIA FOR COMING OFF-TREATMENT

Off-treatment criteria mainly apply to eligibility for repeat Descartes-30 treatments. Patients will be taken off treatment for the following:

- DLT as defined in Section 8.1.2 directly attributable to Descartes-30 cells.
- General or specific changes in the patient's condition rendering the patient ineligible for further treatment in the judgment of the investigator.

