8.1.2 DOSE LIMITING TOXICITY (DLT)

Following reactions within 4 hours of Descartes-30 infusion will be considered as DLT:

1. Addition of a third vasopressor
2. Increase in vasopressor dose over baseline greater than or equal to the following:
 - a. Norepinephrine: 1.5 μ g/kg per min
 - b. Phenylephrine: 100 μ g/kg per min
 - c. Dopamine: 10 μ g/kg per min
 - d. Epinephrine: 1 μ g/kg per min
 - e. Vasopressin: 0.04 IU/min
3. Hypoxemia requiring an increase over baseline in FiO_2 of ≥ 0.2 and/or increase in positive end-expiratory airway pressure level of 5 cm H₂O or more to maintain transcutaneous oxygen saturations in an acceptable range based on PI's discretion
4. New cardiac arrhythmia requiring cardioversion (chemical or electrical)
5. New ventricular tachycardia, ventricular fibrillation, or asystole
6. Death

Also, any Grade 3-5 toxicity probably or definitely attributed to Descartes-30 will be a DLT.

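### A related Grade 3-4 toxicity falls under two dosing rules that point opposite ways, hold and re-dose (7.1.2.1) or stop (7.1.2.5), and precedence is not stated expressly

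*Combined protocol and SAP*

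**What the plan says.** **The hold rule.** Section 7.1.2.1 applies to toxicities judged probably or definitely related. The next dose is "delayed until these toxicities have resolved to at least Grade 2". An override lets dosing go ahead sooner if the site investigator and the medical monitor both record that they consider this reasonable. A delay beyond 96 hours ends treatment. The section does not mention DLTs or Section 7.1.2.5. It also contains a general discretion: "Infusions can be delayed up to 96 hours based on PI discretion".

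**The DLT definition.** Section 8.1.2 has two limbs. The first lists acute events: "Following reactions within 4 hours of Descartes-30 infusion will be considered as DLT". It carries no causality test. The second is by grade: "any Grade 3-5 toxicity probably or definitely attributed to Descartes-30 will be a DLT".

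**The stop rule.** Section 7.1.2.5, which concerns eligibility for repeat infusions, takes a patient off treatment for a "DLT as defined in Section 8.1.2 directly attributable to Descartes-30 cells". It has no exception for resolution and no override.

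**Text that touches both.** The Study Intervention part of the synopsis provides for two more infusions "unless they meet the criteria for holding dose or discontinuing study treatment". Footnote a of Table 1 (Section 4.3) sends the reader to 7.1.2.2 for delay and 7.1.2.4 for discontinuation. Those sections cover product administration and ventilator weaning.

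**The concern.** Both rules decide whether a patient who has had a related toxicity receives the next infusion. If they cover the same events, one tells the site to wait and re-dose and the other tells it to stop.

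This is a patient-safety matter first: a patient could be re-exposed after a dose-limiting event that the protocol elsewhere treats as the end of treatment. It would also make exposure after a DLT differ between patients and sites in a multi-center trial, for reasons unrelated to the patients. Section 7.1.2.1 is the text a site would consult at the bedside. It reads as complete in itself, with its own release condition, override and time limit.

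**Working it through.** The protocol states no figure on this point. The check sets the rules side by side by grade, then sizes the difference from Table 1.

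**Step 1: which events each rule reaches.** Take a toxicity judged probably or definitely related, arising after infusion 1 or 2. Read the release condition as Grade 2 or lower, and Grade 5 as death.

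| Grade | 7.1.2.1 (hold) | 8.1.2 (grade limb) | 7.1.2.5 (stop) |
|---|---|---|---|
| 1-2 | Condition already met; no effect | Not a DLT | Not triggered by this limb |
| 3-4 | Hold; release at Grade 2 within 96 hours, or earlier by override | DLT | Off treatment if *directly attributable* |
| 5 | No re-dosing question | DLT | No re-dosing question |

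The release condition has effect only in the Grade 3-4 row, and every event in that row is a DLT.

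**Step 2: what *directly attributable* could mean.**
- If it means probably or definitely related, every event the release clause can govern is also an off-treatment event. The clause and its override then have no case of their own.
- If it is narrower, for example definite only, probably related events could be held and definite ones stopped. The rules still conflict for definitely related Grade 3-4 events, because 7.1.2.1 names those too.
- If it is meant only to filter the 4-hour reactions, which carry no causality test, that is sensible for the first limb. The grade limb already has its own test, so the overlap there remains.

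The overlap therefore exists under each reading for definitely related events. For probably related events it depends on the undefined phrase.

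**Step 3: size per patient.** Three equal infusions are planned, so the dose remaining is 2/3 (67%) after infusion 1 and 1/3 (33%) after infusion 2. From the target doses in Table 1, in millions of cells:

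| Level | Per infusion | Total | Remaining after infusion 1 | Remaining after infusion 2 |
|---|---|---|---|---|
| 1 | 100 | 300 | 200 | 100 |
| 2 | 300 | 900 | 600 | 300 |
| 3 | 600 | 1,800 | 1,200 | 600 |
| 4 | 1,200 | 3,600 | 2,400 | 1,200 |

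After infusion 3 nothing remains and there is no conflict. The Level 4 row applies only to patients dosed there: 3 to 6 in Arm 1, plus up to 12 + 12 = 24 in Arm 2 if that dose is chosen. The documents give no rate for related Grade 3-4 events, so no frequency can be attached.

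**Step 4: effect on the MTD.** Section 4.5 counts patients with a DLT "considered probably or definitely related to Descartes-30" within 7 days of the first dose. If the first event falls inside that window, the patient is already counted and a second event adds nothing. If it falls outside, any event after a later infusion falls outside too. The count is the same whichever dosing rule is followed.

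**The case against.** The strongest reply is that the rules can be read together. Section 7.1.2.1 says when a dose must wait; 7.1.2.5 says who may no longer be dosed, in mandatory terms. The synopsis makes later infusions conditional on meeting neither the holding nor the discontinuing criteria, so a patient who meets 7.1.2.5 should receive no more. Section 7.1.2.1 itself adds that, during the hold, the team assesses whether the patient qualifies for infusion, so reaching Grade 2 is not stated to be enough. The extra causality words in 7.1.2.5 may also be a deliberate, narrower test.

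Much of this stands. A reader might infer that the protocol sets out to re-dose patients after a DLT, or that nothing in it bears on the choice. The documents do not support either: the balance of the text favours discontinuation, and 7.1.2.5 does require a single patient with a qualifying DLT to stop. A reader might also infer that the MTD is compromised; step 4 of the working shows it is not.

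What does not stand is that this settles the matter. The synopsis names both sets of criteria without ranking them. The eligibility sentence in 7.1.2.1 mentions neither DLTs nor 7.1.2.5. If discontinuation always prevails for related DLTs, the Grade 2 release and the two-physician override have nothing to govern, and a site may reasonably assume they were written for some purpose. A narrower causality test still leaves definitely related events under both rules.

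Other safeguards help but do not decide the case. The override needs documented agreement from two physicians, the investigator may stop treatment on judgement, and Section 8.5 pauses the study after two subjects with related Grade 3-4 vital-organ events. Section 6.2 also refers to a handling manual that is not among the documents; it may contain clarifying text.

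**Conclusion.** The point holds as a conflict without express precedence. For a definitely related Grade 3-4 toxicity after infusion 1 or 2 that falls to Grade 2 within 96 hours, or is overridden, 7.1.2.1 permits the next infusion and 7.1.2.5 ends treatment. The same applies to probably related events unless *directly attributable* is meant to exclude them. The better reading is that treatment stops, but the site has to work that out, and the Table 1 footnote misdirects it.

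The difference per patient is one or two of three infusions, from 100 million cells (Level 1, after infusion 2) to 2,400 million (Level 4, after infusion 1). This rests on reading the release threshold as Grade 2 or lower and on the documents alone. It is a safety ambiguity that should be corrected; it does not threaten the primary endpoint.

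**What to change.** 1. In 7.1.2.1, state that a patient who meets 7.1.2.5 receives no further infusion, and that neither resolution to Grade 2 nor the two-physician override restores eligibility.
2. In 7.1.2.5, replace *directly attributable* with the probably-or-definitely-related standard used in 4.5, 7.1.2.1, 8.1.2 and 8.5. This still filters 4-hour reactions unrelated to the cells.
3. Changes 1 and 2 leave the Grade 2 release clause and its override with no case to govern. Delete them, or rewrite them for toxicities that are not DLTs. The existing investigator discretion to delay by up to 96 hours already covers lesser events.
4. Correct footnote a of Table 1 to cite 7.1.2.1 and 7.1.2.5.

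The cost is an amendment to two sections and one footnote, plus a clinical consequence: some patients whose related toxicity settles quickly lose one or two infusions. If the sponsor meant *directly attributable* to be narrower, change 2 also tightens the off-treatment threshold for probably related DLTs. The sponsor should make that choice knowingly. If it prefers to keep hold-and-release for those cases, it should define the phrase and say so.
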